641    Hyperglycemia not associated with an Adverse Device Effect is only reportable as an adverse  
642    event when one of the following 4 criteria is met:

643        the event involved DKA, as defined by the Diabetes Control and Complications Trial  
644        (DCCT) and described below  
645        evaluation or treatment was obtained at a health care provider facility for an acute event  
646        involving hyperglycemia or ketosis  
647        blood ketone level  $\geq 0.6$  mmol/L and communication occurred with a health care provider at  
648        the time of the event

649        blood ketone level  $\geq 2.5$  mmol/L, even if there was no communication with a health care  
650        provider

651        Hyperglycemic events are classified as DKA if the following are present:

652        Symptoms such as polyuria, polydipsia, nausea, or vomiting;

653        Serum ketones  $> 1.5$  mmol/L or large/moderate urine ketones;

654        Either arterial blood pH  $< 7.30$  or venous pH  $< 7.24$  or serum bicarbonate  $< 15$ ; and

655        Treatment provided in a health care facility

656        All reportable Adverse Events—whether volunteered by the participant, discovered by study  
657        personnel during questioning, or detected through physical examination, laboratory test, or other  
658        means—will be reported on an adverse event form online. Each adverse event form is reviewed  
659        by the Sponsor to verify the coding and the reporting that is required.

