Contains trade secrets and/or confidential information exempt from disclosure from 21 CFR 20.61

	automated initialization and adaptation system, as well as the use of Closed-Loop Control.
Study Population	Male and female subjects $\geq$ 18 years of age with type 1 diabetes, who are current MDI users, who have a baseline A1c at screening between 7.5 to 11%
Number of Subjects	Up to 45 subjects may sign the consent form and be screened, with the goal that 30 subjects start use of the study device, and at least 20 subjects complete the trial.
Number of Sites	1 clinical site in the United States
Main Criteria for Inclusion	
Eligibility to enroll in the study will be assessed based on the following inclusion criteria:
 
 
1. Adult subjects <math>\geq</math> age 18 years
 
2. Clinical diagnosis of type 1 diabetes for at least one year
 
3. Using a basal/bolus regimen by injection (MDI therapy)
 
4. Total daily dose <math>\geq</math> 10 units/day
 
5. Willing to use only aspart (novolog) or lispro (humalog) U-100 insulin with the study pump.
 
6. A1c <math>\geq</math> 7.5% and <math>\leq</math> 11% at screening
 
7. Not pregnant or planning a pregnancy during the time period of the study.
 
8. Has current glucagon product to treat severe hypoglycemia (injectable or nasal) at home (will provide prescription if they do not have one)
 
9. Willingness to follow study procedures and a signed informed consent form
 

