Main Criteria for Exclusion	
Eligibility to enroll in the study will be assessed based on the following exclusion criteria:
 
 
1. Two or more episodes of severe hypoglycemia (needing assistance) in the past 6 months
 
2. Two or more episodes of diabetic ketoacidosis in the past 6 months
 
3. Inpatient psychiatric treatment in the past 6 months
 
4. History of drug abuse (defined as any illicit drug use) or history of alcohol abuse prior to screening or unwillingness to agree to abstain from illicit drugs throughout the study
 
5. Significant chronic kidney disease or hemodialysis
 
6. Significant liver disease
 
7. History of adrenal insufficiency
 
8. History of abnormal TSH consistent with hypothyroidism or hyperthyroidism that is not appropriately treated
 
9. Other chronic disease/condition determined by investigator to interfere with participation in the study
 
10. Use of glucocorticoids, beta blockers or other medications determined by investigator to interfere with study
 

Confidential

Contains trade secrets and/or confidential information exempt from disclosure from 21 CFR 20.61

	
11. Use of long-acting insulin, inhaled insulin (Afrezza), or use of any non-insulin glucose lowering agents (i.e. SGLT-2 inhibitor) other than Metformin with the study pump
 
12. Subject is pregnant or lactating or intending to become pregnant before or during participation in this study.
 
13. Investigator judgement that subject would not be able to complete the trial.

Procedures in Screening/Baseline Period	At screening, baseline data will be collected. For Dexcom G6 users, mean/median sensor glucose, TIR and all glycemic outcomes will be recorded as baseline data if data is available for the at least 11 of the last 14 days. Those without adequate baseline data will collect Dexcom G6 sensor data to establish a baseline over the next 2 weeks.
Management of Adverse Events	Safety information will be collected weekly during study clinic phone calls, or more frequently if a severe AE occurs. The event, date of onset, severity, seriousness, duration and relationship to the device/adaptation system will be documented. All reported device-related AEs will be followed until they are adequately resolved or stabilized, or until study completion/termination, whichever comes first.

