### 226 **5.3 STUDY ENDPOINTS**

227 1) Primary Endpoint:

- 228 a. To demonstrate the safety of the system, by assessing the number of severe  
229 hypoglycemic events (needing assistance) compared to expected incidence

230 2) Secondary Endpoints:

- 231 a. Time in range 70-180 mg/dL
- 232 b. Time < 54 mg/dL
- 233 c. Time < 70 mg/dL
- 234 d. Time > 180 mg/dL
- 235 e. Time > 250 mg/dL
- 236 f. Time in tight glycemic range 70-140 mg/dL
- 237 g. Post-prandial glycemic peak
- 238 h. 4-hour post meal glucose AUC
- 239 i. Sensor glucose median and interquartile range
- 240 j. CGM metrics daytime vs. nighttime
- 241 k. CGM metrics compared each week after adaptation
- 242 l. DKA
- 243 m. Serious Adverse Events
- 244 n. Adverse Device Effects
- 245 o. Change in total daily insulin use, basal and bolus
- 246 p. Number of physician overrides/physician initiated changes in pump settings
- 247 q. Patient Reported Outcomes

248 **6 SUBJECT SELECTION**

249 **6.1 SUBJECT POPULATION**

250 **6.1.1 INCLUSION CRITERIA:**

251 Eligibility to enroll in the study will be assessed based on the following inclusion criteria:

- 252 1) Adult subjects  $\geq$  age 18 years
- 253 2) Clinical diagnosis of type 1 diabetes for at least one year
- 254 3) Using a basal/bolus regimen by injection (MDI therapy)
- 255 4) Total daily dose  $\geq$  10 units/day
- 256 5) Willing to use only aspart (novolog) or lispro (humalog) U-100 insulin with the study  
257 pump.
- 258 6) A1c  $\geq$  7.5% and  $\leq$  11% at screening
- 259 7) Not pregnant or planning a pregnancy during the time period of the study.
- 260 8) Has current glucagon product to treat severe hypoglycemia (injectable or nasal) at home  
261 (will provide prescription if they do not have one)
- 262 9) Willingness to follow study procedures and a signed informed consent form

263 **6.1.2 EXCLUSION CRITERIA:**

264 Eligibility to enroll in the study will be assessed based on the following exclusion criteria:

- 265 1) Two or more episodes of severe hypoglycemia (needing assistance) in the past 6 months
- 266 2) Two or more episodes of diabetic ketoacidosis in the past 6 months
- 267 3) Inpatient psychiatric treatment in the past 6 months
- 268 4) History of drug abuse (defined as any illicit drug use) or history of alcohol abuse prior to  
269 screening or unwillingness to agree to abstain from illicit drugs throughout the study
- 270 5) Significant chronic kidney disease or hemodialysis
- 271 6) Significant liver disease

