## 409 **7.8 POST STUDY PHONE CALL**

410 All participants will have a post-study phone call 3 ( $\pm 1$ ) days after the date of their final visit and  
411 transition back to their prior insulin therapy, during which the following will occur:

412 • Check on transition back to usual home diabetes care

413 • Assessment of adverse events

414

---

Confidential

Contains trade secrets and/or confidential information exempt from disclosure from 21 CFR 20.61

415 **8 STATISTICAL CONSIDERATIONS**

416 **8.1 STATISTICAL ANALYSIS:**

417 This feasibility study is a prospective, single arm study, evaluating al algorithm to recommend  
418 insulin pump settings at pump start (initialization) and then weekly for 13 weeks.

419 Descriptive statistics of the rates of severe hypoglycemia, DKA, and serious adverse events will  
420 be reported for baseline (with CGM run-in data) and compared to changes after each weekly  
421 adaptation. Additionally, descriptive statistics of glycemic outcomes will for baseline and each  
422 intervention configuration will be provided.

423 The statistics will include all primary and secondary outcomes of the study as listed in section  
424 5.3. These statistics will be calculated at the patient-level, and a sub-analysis of daytime vs.  
425 nighttime statistics will be provided.

426

427

428 **9 RISKS AND BENEFITS**

429 **9.1 POTENTIAL RISKS AND BENEFITS OF THE DEVICE**

430 Risks and Benefits are detailed below. Loss of confidentiality is a potential risk; however, data  
431 are handled to minimize this risk. Hypoglycemia, hyperglycemia and ketone formation are  
432 always a risk in participants with diabetes and participants will be monitored for this.

433 **9.2 VENIPUNCTURE RISKS**

434 A hollow needle/plastic tube may be placed in the arm for taking blood samples. Blood draws  
435 can cause some common reactions like pain, bruising, or redness at the sampling site. Less  
436 common reactions include bleeding from the sampling site, formation of a small blood clot or  
437 swelling of the vein and surrounding tissues, and fainting.

438 **9.3 FINGERSTICK RISKS**

439 About 1 drop of blood will be removed by fingerstick for measuring blood glucose and  
440 sometimes Hemoglobin A1c (HbA1c) or other tests. This is a standard method used to obtain  
441 blood for routine hospital laboratory tests. Pain is common at the time of lancing. In about 1 in  

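### Does the lack of a meal or bolus record while subjects inject leave the post-meal and insulin-change endpoints without a usable baseline?

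*Combined protocol and SAP*

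**What the plan says.** Section 8.1 contains two relevant sentences. One begins "Additionally, descriptive statistics of glycemic outcomes will for baseline and each" and goes on to the intervention configurations. The other is "The statistics will include all primary and secondary outcomes of the study as listed in section" 5.3. The synopsis row on the screening and baseline period says, for existing Dexcom G6 users with enough data, that "mean/median sensor glucose, TIR and all glycemic outcomes will be recorded as baseline data". Subjects without enough data wear a G6 for two weeks.

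Section 5.3 lists, among 17 secondary endpoints (a to q), g "Post-prandial glycemic peak", h "4-hour post meal glucose AUC" and o "Change in total daily insulin use, basal and bolus".

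Before the pump starts, subjects are on injections: section 6.1.1 requires "Using a basal/bolus regimen by injection (MDI therapy)" and the synopsis describes people "who are current MDI users". Table 1 in section 7.4 has rows for CGM assessment and device downloads, but none for meals or injected doses.

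**The concern.** A post-meal peak or AUC cannot be computed from a glucose trace without meal times. Read literally, section 8.1 and the synopsis promise g and h at baseline, yet the only time-stamped records described for that period are glucose data. Section 9.8 mentions a home-pump download, which people on injections would not have.

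Two further points are open. For the pump period, the plan does not say which meals count or whether AUC is total or incremental. For o, it names no reference value for the change. The injected dose, the total on the start worksheet and the first pump days are all conceivable. If analysts chose differently, the reported direction for h or o could differ, and a larger sample would not remove the difference.

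**Working it through.** **1. What the baseline promise covers.** The baseline sentence in section 8.1 covers glycemic outcomes, and the sentence before it covers safety-event rates. Insulin use is neither. The sentence that takes in all of 5.3 does not mention baseline. It cannot require a baseline value for every item, because p (physician overrides of pump settings) has none before the pump starts. The literal promise therefore reaches g and h, but not o.

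**2. Meal times for g and h.** None are described before the pump. On the pump, the sample adaptation report in section 4.3 (Figure 2) estimates post-meal low-glucose probabilities from uploaded data, so meals can be located in the pump record. A week-by-week series after pump start is possible; a comparison with the injection period is not.

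**3. Insulin dose before the pump.**
- Basal: the Figure 1 worksheet takes the daily long-acting dose, with a 7-day average recommended.
- Total: inclusion criterion 4 (at least 10 units/day) requires it to be ascertained at screening.
- Records: section 7.4 puts previous therapy on the eCRF, section 5.2 lists therapy data and allows the run-in to be repeated to watch insulin dose, and section 7.7 has staff return to the baseline therapy doses.
- Bolus: not recorded directly, but available as total minus basal.

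**4. Size of the reference-value question for o.** The worksheet example reproduces: 35/24 = 1.458, shown as 1.46 units/hour. Its total of 58 units/day is calculated from the 35-unit long-acting dose alone, so the implied bolus of 58 − 35 = 23 units (23/58 = 39.7%) is a formula result. With assumed true basal shares of 40%, 50% and 60%, and an assumed on-pump total of 64 units/day:

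| Basal share | True total = 35/share | Worksheet minus true | Change to 64, from true | Change to 64, from worksheet |
|---|---|---|---|---|
| 40% | 87.5 | −29.5 (−33.7%) | −23.5 | +6 |
| 50% | 70.0 | −12.0 (−17.1%) | −6.0 | +6 |
| 60% | 58.3 | −0.3 (−0.6%) | +5.7 | +6 |

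The signs differ only when the on-pump total lies between 58 and the true total, and 64 was chosen inside that interval for the first two rows. Below 58, every reference in the table gives a fall; above 87.5, every one gives a rise. At a 60% share the two answers nearly coincide. Figure 1 lists the worksheet total among the Control-IQ settings, as a value needed to switch the system on, and nothing calls it a baseline.

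**5. Size of the AUC question for h.** Over 4 hours, total AUC = 4 × (pre-meal level + mean rise) and incremental AUC = 4 × mean rise. Assume the pre-meal level goes from 190 to 150 mg/dL and the mean rise from 30 to 40.
- Total: 4 × 220 = 880 to 4 × 190 = 760 mg·h/dL, which is −120/880 = −13.6%.
- Incremental: 4 × 30 = 120 to 4 × 40 = 160 mg·h/dL, which is +40/120 = +33.3%.

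Opposite signs of this kind need a rise that grows while the pre-meal level falls by more. All four glucose inputs are assumed. Section 5.3 says glucose AUC without qualification, and the plain reading is total AUC.

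**6. What depends on g, h and o.** The secondary objective in section 5.1 names time-in-range metrics, adverse events and physician overrides. The primary objective concerns severe hypoglycemia. None of these uses g, h or o.

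**The case for a change.** The best argument for amending the plan is that meal times and injected bolus doses not logged before training may be lost for good, and that definitions chosen after seeing data leave room for selective reporting. Descriptive reporting does not make an undefined quantity defined. The synopsis says the outcomes will inform the product configuration, and the edit is cheap: a text amendment with IRB approval and no new visits.

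Part of this stands. Baseline g and h have no stated source, and confining them to the pump period falls short of the literal wording in section 8.1 and the synopsis. The reference point for o and the way injected bolus is recorded are also unstated.

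It does not carry further. No stated rule produces a wrong number. The sensible readings are close at hand: pump-period data for g and h, total AUC for h, and recorded injection doses or pump downloads for o. The sign reversals show what is possible with selected inputs, not what is likely. No test, sample size or decision rule uses these endpoints, and case report forms outside the documents may already hold the dose fields.

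**Conclusion.** No change to the plan is needed. The gap is missing detail on 3 of 17 descriptive secondary endpoints in a single-arm feasibility study that aims for up to 30 device starters and at least 20 completers. What is lost is a comparison of post-meal glucose between injections and pump; the series within pump use remains available. For o, basal dose has a stated source, total dose an implied one and bolus follows by subtraction, so only the choice of reference is open. The results can state that choice.

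This rests on three assumptions: pump records locate meals, as the adaptation report implies; the total dose ascertained for eligibility is kept; and the worksheet total is not taken as a baseline. The basal shares, the on-pump total and the glucose values above are illustrative.

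Three nearby items are separate clerical matters and do not alter this conclusion. Section 7.4 refers to randomization in a single-arm study, section 9.8 refers to a home pump in people on injections, and central-lab HbA1c is drawn at training and week 13 without being named in section 5.3.

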## 660        **11.5 RELATIONSHIP OF ADVERSE EVENT TO STUDY DEVICE**

661        The study investigator will assess the relationship of any adverse event to be related or unrelated  
662        by determining if there is a reasonable possibility that the adverse event may have been caused  
663        by the study device.

664        To ensure consistency of adverse event causality assessments, investigators should apply the  
665        following general guideline when determining whether an adverse event is related:

666        Yes

667        There is a plausible temporal relationship between the onset of the adverse event and the study  
668        intervention, and the adverse event cannot be readily explained by the participant's clinical state,  
669        intercurrent illness, or concomitant therapies; and/or the adverse event follows a known pattern  
670        of response to the study intervention; and/or the adverse event abates or resolves upon  
671        discontinuation of the study intervention or dose reduction and, if applicable, reappears upon  
672        re-challenge.

673        No

674        Evidence exists that the adverse event has an etiology other than the study intervention (e.g.,  
675        preexisting medical condition, underlying disease, intercurrent illness, or concomitant  
676        medication); and/or the adverse event has no plausible temporal relationship to study  
677        intervention.

## 678        **11.6 INTENSITY OF ADVERSE EVENT**

679        The intensity of an adverse event will be rated on a three point scale: (1) mild, (2) moderate, or  
680        (3) severe. It is emphasized that the term severe is a measure of intensity: thus a severe adverse  
681        event is not necessarily serious. For example, itching for several days may be rated as severe, but  
682        may not be clinically serious.

683 MILD: Usually transient, requires no special treatment, and does not interfere with the participant's  
684 daily activities.

685 MODERATE: Usually causes a low level of inconvenience or concern to the participant and may interfere  
686 with daily activities, but is usually ameliorated by simple therapeutic measures.

687 SEVERE: Interrupts a participant's usual daily activities and generally requires systemic drug therapy or  
688 other treatment.

## 689 **11.7 CODING OF ADVERSE EVENTS**

690 Adverse events will be coded using the MedDRA dictionary. The investigator's assessment will  
691 be recorded.

692 Adverse events that continue after the participant's discontinuation or completion of the study  
693 will be followed until their medical outcome is determined or until no further change in the  
694 condition is expected.

## 695 **11.8 OUTCOME OF ADVERSE EVENT**

696 The outcome of each reportable adverse event will be classified by the investigator as follows:

697 RECOVERED/RESOLVED – The participant recovered from the AE/SAE without sequelae.  
698 Record the AE/SAE stop date.

699 RECOVERED/RESOLVED WITH SEQUELAE – The event persisted and had stabilized  
700 without change in the event anticipated. Record the AE/SAE stop date.

701 FATAL – A fatal outcome is defined as the SAE that resulted in death. Only the event that was  
702 the cause of death should be reported as fatal. AEs/SAEs that were ongoing at the time of death;  
703 however, were not the cause of death, will be recorded as “resolved” at the time of death.

704 NOT RECOVERED/NOT RESOLVED (ONGOING) – An ongoing AE/SAE is defined as the  
705 event was ongoing with an undetermined outcome.

706 An ongoing outcome will require follow-up by the site in order to determine the final outcome of  
707 the AE/SAE.

708 The outcome of an ongoing event at the time of death that was not the cause of death, will be  
709 updated and recorded as “resolved” with the date of death recorded as the stop date.

710 UNKNOWN – An unknown outcome is defined as an inability to access the participant or the  
711 participant's records to determine the outcome (for example, a participant that was lost to follow-  
712 up).

713 All clinically significant abnormalities of clinical laboratory measurements or adverse events  
714 occurring during the study and continuing at study termination should be followed by the  
715 participant's physician and evaluated with additional tests (if necessary) until diagnosis of the  
716 underlying cause, or resolution. Follow-up information should be recorded on source documents.

717 If any reported adverse events are present when a participant completes the study, or if a  
718 participant is withdrawn from the study due to an adverse event, the participant will be contacted  
719 for re-evaluation within 2 weeks. If the adverse event has not resolved, additional follow-up will  
720 be performed as appropriate. Every effort should be made by the Investigator or delegate to  
721 contact the participant until the adverse event has resolved or stabilized.

## 722 **11.9 REPORTABLE DEVICE ISSUES**

723 All UADEs, ADEs, device complaints, and device malfunctions will be reported irrespective of  
724 whether an adverse event occurred, except in the following circumstances.

725 The following device issues are anticipated and will not be reported on a Device Issue Form but  
726 will be reported as an Adverse Event if the criteria for AE reporting described above are met:

- 727 1) Component disconnections
- 728 2) CGM sensors lasting fewer than the number of days expected per CGM labeling
- 729 3) CGM tape adherence issues
- 730 4) Pump infusion set occlusion not leading to ketosis
- 731 5) Battery lifespan deficiency due to inadequate charging or extensive wireless  
732 communication
- 733 6) Intermittent device component disconnections/communication failures not leading to  
734 system replacement
- 735 7) Device issues clearly addressed in the user guide manual that do not require additional  
736 troubleshooting
- 737 8) Skin reactions from CGM sensor placement or pump infusion set placement that do not  
738 meet criteria for AE reporting

